Outreach strategy: As mentioned above, we previously conducted a randomized comparative effectiveness trial that demonstrated the potential for mailed invitation to use and return an enclosed FIT kit, with telephone follow up to promote completion, to increase screening rates compared to usual care. In our pilot work, we have adapted the mailed FIT strategy for use at FQHCs, and, in the process, also address several potential limitations of the prior work. The new proposed strategies that were modified include: 1) mailed invitation to complete an enclosed FIT in English and Spanish, 2) low literacy pictorial home-based FIT completion instructions, 3) FIT result reporting to patient and primary provider via culturally sensitive means (e.g., by phone and in person, not via mail), and 4) telephone assistance with colonoscopy referral and completion for individuals with abnormal FIT. To improve on the prior strategy, first, telephone assistance will be done by SYHC-based patient navigator, whereas in our prior work telephone assistance was done by a university-based nurse and medical assistance. Second, we have revised our English and Spanish-language invitation letters for use in SYHC’s clinic population, that is largely a low income, unacculturated and low literacy population. Third, we will streamline the phone follow up required. The prior intervention utilized two automated, and up to two live telephone calls within 3 weeks of mailed invitation to promote screening. Because automated phone reminders may not be able to be reliably implemented across FQHCs, we will not include this approach in the intervention. Further, an increased, 4-5 week window for delivery of reminder phone calls will be allowed to increase the chances of feasible implementation. Fourth, we will develop a process for referring individuals with abnormal FIT for diagnostic colonoscopy outside of SYHC based on best practices currently utilized by the clinic for breast and cervical cancer screening and follow-up. This step is critical, because FQHCs generally have to refer elsewhere for specialty services. Prior to initiation of the randomized trial, we will, in additional preparation to research work, conduct a focus group with a random sample of 30 patients meeting inclusion/exclusion criteria (men and women, age 50 to 75, not up-to-date with screening) recruited from SYHC waiting rooms to review the interventions and study materials to help fine tune the outreach strategy. As part of this process, we will procure feedback on additional features (such as inclusion of links to internet videos on how to complete the FIT kits, timing of follow phone calls during the day/evening) that might improve the effectiveness of the mailed FIT strategy.

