
Inreach strategy: We have similarly adapted prior inreach strategies tested by our group in the past for the specific goal of promoting CRC screening awareness and completion.(38) For example, lessons learned from a prior breast cancer navigation study used by the partnership at SYHC show that the average patient load a navigator can manage per week is roughly 10 to 12 given the extended time needed for one-on-one patient empowerment, motivation, education, and follow-up to link patients with appropriate care. In addition, the

navigation assistance required to initiate screening is quite often less than that required for follow-up to abnormal exams (e.g., which requires diagnostic colonoscopy at an external specialty care site and the potential for cancer treatment) due to the individual psychosocial barriers associated with seeking treatment (e.g., disbelief in efficacy of treatment, myths about cancer, unawareness of resources available etc). This research suggests that culturally appropriate interventions such as in-depth patient navigation can facilitate Latinas' successful entry into, and progression through, the cancer care system and improve time from screening to diagnosis. As with our mailed FIT strategy, prior to initiation of the randomized trial, we will conduct a focus group with a random sample of 30 individuals meeting inclusion/exclusion criteria for the trial to review the interventions and study materials to help fine tune the inreach strategy.

Pilot work summary. Our pilot work demonstrates that the proposed work is feasible, that we are fully committed to seeing the work through, and that we have taken significant steps to optimize our proposed strategies for the target population. Though our prior work and pilot work has been substantial, we recognize several limitations that we will address in the process of the current work. First, while we have developed our intervention and intervention materials through community-based participatory research strategies, guided by prior work and pilot work, we have not yet pretested the near-final versions among individuals sampled from the target population. Second, key informant patient interviews were conducted among women, but have yet to be conducted among men. These two limitations will be addressed as part the research approach outlined below.

INNOVATION

The proposed research is innovative for several reasons:

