RCT inclusion/exclusion criteria. We will **include** individuals age 50 to 75 years, with one or more SYHC visits in the last year, at average-risk for CRC but not up-to-date with screening, insured by a MediCal provider, Medicare, or private health insurance. We will **exclude** individuals with personal history of CRC or colorectal polyps, as well as the uninsured. Uninsured individuals will be excluded because in absence of health insurance, we cannot guarantee that screening (and cancer care if CRC is found) will be financially possible. Inclusion and exclusion criteria will be applied through queries of the SYHC EHR.

Identification of candidate patients and recruitment. Using the SYHC EHR we will enroll and randomize 648 individuals meeting inclusion/exclusion criteria: 162 to usual care, inreach, mailed FIT outreach, and the

inreach strategy plus FIT outreach, respectively (see sample size and power calculations below). A waiver of documentation of informed consent will be obtained for randomization and intervention delivery based on two primary factors: 1) goal of increasing screening for as many individuals as possible, and 2) scientific advantage of observing as close to “real world” impact of the planned strategies on a sample of patients. We reviewed with our Institutional Review Board a potential strategy for complete waiver of informed consent, but were advised that maximizing patient autonomy and awareness of potential loss of confidentiality associated with research data collection merited at minimum a one-page informational research “fact sheet” that would provide patients with information about the research project. In the letter, patients will be the option to specifically note a desire not to participate in the intervention or subsequent data collection. Recruitment will continue until a sample size of 162 individuals per group who do not opt out of the research is achieved. In our primary, intent to screen analysis, we will analyze all randomized individuals who do not opt out of the research.

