The EHR will be queried 4 times over a 1 year period. At time of each query 1/4 of the target sample will be identified and randomized, and have the assigned interventions initiated. Each group will be followed for 12 months for the primary outcome: completion of any CRC screening test (guaiac fecal occult blood test, FIT, sigmoidoscopy, or colonoscopy), measured by evidence of screening documented within the EHR. Thus, the total recruitment period will last 12 months, and the duration through completion of 6 month follow up of all patients will be 24 months. Measurements will include demographic information (race, ethnicity, sex, and age), number and location of health center visits, primary provider, and comorbid medical conditions. In secondary analyses, we will determine whether screening rates vary across these characteristics, and also assess whether for significant interactions between characteristics and intervention effects.

Analytic approach and sample size, Aim 1. We estimated the sample size for 5 comparisons (usual care vs. inreach, usual care vs. outreach, usual care vs. inreach + outreach, inreach + outreach vs. outreach alone, and inreach + outreach vs. inreach alone), assuming $\alpha = 0.01$ across all groups and power ≥ 0.8 . For these assessments, we assumed the following rates of screening on follow up among individuals not up to date at baseline: 10% for usual care, 25% for inreach, 25% for outreach, 45% for inreach + outreach combined. The 10% rate for usual care and 25% estimate for outreach were conservative assumptions based on our previously cited work (30). The 25% rate for inreach was a conservative estimate based on observations that inreach interventions such as patient navigation have boosted screening completion (among patients referred for colonoscopy) by 41 to 78%. Finally, the 45% rate for both interventions combined was considered the minimal clinically significant difference that would justify implementing two different interventions for increasing screening. Under these assumptions, we computed need for a sample size of $n=648$ patients ($n=162$ for each group) to have sufficient power for all primary comparisons of interest.

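### The primary outcome is read only from the health center's EHR, with no outcome search common to all arms, so endoscopies done elsewhere may be recorded more often in the inreach arms than in usual care

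*Combined protocol and SAP*

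**What the plan says.** **Outcome and its source.** Under Identification of candidate patients and recruitment, the primary outcome is any guaiac test, FIT, sigmoidoscopy or colonoscopy, "measured by evidence of screening documented within the EHR". No second source is named: no claims, no request for outside records, no patient query. Analytic approach and sample size, Aim 1 lists the same tests and ties completion to the 12 months after randomization. The Overview gives 6 months for the same outcome.

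**Where endoscopy is done.** Under Pilot Research, Outreach strategy: "FQHCs generally have to refer elsewhere for specialty services".

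**Who has navigator contact.** The Specific Aims define inreach as based on patient navigation. For outreach, "telephone assistance will be done by SYHC-based patient navigator", including reminder calls and "telephone assistance with colonoscopy referral and completion for individuals with abnormal FIT". No comparable contact is described for usual care.

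**Safeguards.** The statistician receives a deidentified dataset from SYHC (Data Management and Quality Control). No arm-blind outcome review is described. Threats to Validity discusses contamination but not outcome ascertainment.

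**The concern.** A stool test processed through SYHC should reach the chart in the same way in every arm. An endoscopy done elsewhere reaches it only if a report comes back or someone at SYHC learns of the test and records it. Regular contact with a navigator makes both more likely. If that happens, part of the recorded difference between inreach and usual care is a difference in recording and not in screening. A larger sample does not help either.

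Outside endoscopy is not a side issue for inreach. The 25% rate assumed for that arm is justified by gains from navigation among patients referred for colonoscopy. Hypothesis 1a is the one most exposed. The effect sizes also matter in themselves, because Impact and Next Steps intends them to guide adoption at SYHC and later cost-effectiveness work.

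**Working it through.** **1. The plan's own figure.** Inputs from Analytic approach and sample size, Aim 1: 10% vs 25%, alpha 0.01, power 0.8. Sidedness is not stated; two-sided is assumed. With mean rate 0.175, z = 2.576 and 0.842:

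n₀ = [2.576·√(2·0.175·0.825) + 0.842·√(0.10·0.90 + 0.25·0.75)]² / 0.15² = 148.4

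With continuity correction: n = (n₀/4)·[1 + √(1 + 4/(n₀·0.15))]² = 161.5, so 162 per arm.

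This matches the plan. The sample size is not in question, and 15 points is the planned difference against which to judge any bias.

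**2. Recorded rate under incomplete capture.** Let T be true completion, f the share of completions that are outside endoscopies, and c the probability that an outside test reaches the EHR. Then:

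recorded rate = T·(1 − f + f·c)

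The documents give none of these three values. Assumed: T = 15% in both arms (no true effect), f = 0.20 to 0.50, c = 0.95 with a navigator and 0.50 or 0.70 without. The last column is the chance of a significant result at two-sided 0.01 with 162 per arm (normal approximation).

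| f | c, usual care | Recorded, navigator | Recorded, usual care | Difference (points) | Ratio | Rejection |
|---|---|---|---|---|---|---|
| 0.20 | 0.70 | 14.85% | 14.10% | 0.75 | 1.05 | 1.1% |
| 0.20 | 0.50 | 14.85% | 13.50% | 1.35 | 1.10 | 1.5% |
| 0.35 | 0.70 | 14.74% | 13.43% | 1.31 | 1.10 | 1.4% |
| 0.35 | 0.50 | 14.74% | 12.38% | 2.36 | 1.19 | 2.6% |
| 0.50 | 0.70 | 14.63% | 12.75% | 1.88 | 1.15 | 2.0% |
| 0.50 | 0.50 | 14.63% | 11.25% | 3.38 | 1.30 | 4.7% |

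Example, last row: 0.15·(0.5 + 0.5·0.95) = 0.14625 and 0.15·(0.5 + 0.5·0.50) = 0.1125.

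In patients, this is 162·0.0075 = 1.2 to 162·0.03375 = 5.5 per arm. At the plan's own 10% usual-care rate the difference runs from 0.10·(0.20·0.25) = 0.5 points to 0.10·(0.50·0.45) = 2.25 points.

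**3. Which comparisons are exposed.**

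- Inreach, alone or combined, vs usual care: navigator contact is described on one side only. This is the main exposure.
- Outreach alone vs usual care: weaker. The colonoscopy help follows an abnormal FIT, and such a patient already counts as screened. Only reminder calls that happen to reveal an outside test could add to capture.
- Combined vs outreach alone: smaller, since both arms have navigator contact.
- Combined vs inreach alone: largely absent, since both arms have the inreach navigator.

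**The case against.** The strongest reply is that the mechanism is inferred. Nothing says that navigators enter outside results in the chart, or that usual-care endoscopy reports fail to come back. Usual care is barely described, so the contrast rests partly on silence. CRC screening is a publicly reported measure for these centers (Significance), which gives SYHC a reason to record tests in every arm. The assumed bias is also small beside 15 points. All of this stands and limits the strength of the point. It does not supply an outcome search common to the arms.

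A reader might also infer more than the documents support:

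- **That older outside colonoscopies charted during follow-up would count as completions.** Analytic approach and sample size, Aim 1 requires completion after randomization, so an earlier test does not qualify. Stating that the test date governs only makes this explicit.
- **That the trial's navigators follow each inreach patient to completion.** The phrase "extended time needed for one-on-one patient empowerment, motivation, education, and follow-up to link patients with appropriate care" describes lessons on caseload from a prior breast cancer navigation study. It is background to the inreach strategy, not its procedure.
- **That all the external colonoscopy described is at stake.** The wording "which requires diagnostic colonoscopy at an external specialty care site" concerns follow-up of abnormal exams. After an abnormal FIT the outcome has already been met. Only the general remark on specialty referral supports outside screening endoscopy.
- **That the whole of Hypothesis 1c is biased.** Both of its comparisons have navigator contact on each side.
- **That the bias could reach 12 points, with 62% false rejection.** Those values need 25% true completion, 80% of tests done outside, and capture of 90% vs 30%. Nothing in the documents points to that corner.

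**Conclusion.** The concern holds as a gap in outcome ascertainment, not as a demonstrated bias. Four facts are in the documents: endoscopy counts, the EHR is the only named source, specialty services are generally referred out, and navigator contact is described only for the intervention arms. Unequal capture favoring inreach over usual care is a reasonable inference from them.

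Under the assumptions shown, its size is about 0.8 to 3.4 points with no true effect. The false-positive probability is then 1.1 to 4.7% against a nominal 1%. That would not by itself produce the planned difference, but it could inflate the estimate or tip a borderline result. The true size cannot be derived from the documents. The point is worth settling before outcomes are extracted, because it is hard to repair once follow-up has ended.

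**What to change.** Amend Identification of candidate patients and recruitment, and Analytic approach and sample size, Aim 1:

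1. **One rule for outside endoscopy.** Count it only when a dated procedure report or result is found, with the test date after randomization and inside the outcome window. Find it by one identical EHR search in all four arms, with arm hidden from the person searching, and include the same check of open endoscopy referrals for everyone. An entry that rests only on what a patient told a navigator does not count. The 6- and 12-month statements of the window must be reconciled first.
2. **Show where completions come from.** Report completions by test type and arm. Add a sensitivity analysis of the primary comparisons using only stool tests processed through SYHC. State that it also removes genuine endoscopy gains, so it shows robustness and does not replace the primary analysis. A smaller effect there would not by itself prove recording bias.

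The cost is some added text, one extra analysis of data already held, and a modest amount of record checking among 648 patients. A few true outside tests may go uncounted. Tests arranged without an SYHC referral may still be missed, so the rule reduces unequal capture and may not remove it. Payer claims are an optional addition: all participants are "insured by a MediCal provider, Medicare, or private health insurance", but nothing in the documents shows that SYHC can obtain claims.

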The primary outcome is completion of any CRC screening test (guaiac fecal occult blood test, FIT, sigmoidoscopy, or colonoscopy) within 12 months of randomization. The analytic approach taken will depend on whether or not an interaction exists between the outreach and inreach strategies on screening completion. If no interaction is present, screening rates for inreach vs. usual care and outreach vs. usual care will be compared using a Chi-square test of proportions, requiring $p < 0.01$ for statistical significance. If interaction is noted, we will compare screening rates with a Chi-square test of proportions for inreach without outreach vs. usual care, as well as inreach with outreach vs. usual care separately, using a $p < 0.025$ to indicate statistical significance. In both cases (interaction or no interaction), secondary comparisons will include inreach plus outreach vs. usual care, as well as inreach plus outreach vs. either strategy alone. We will conduct additional analyses treating screening completion as the dependent variable, and examine the relationship of group assignment, demographic characteristics, primary provider, and clinic visit frequency to this outcome. Factors associated with screening completion on univariate analyses will be considered as part of a logistic regression model examining factors independently associated with screening completion; in the case of interaction by group assignment a term for interaction will be included in our models. Additionally, interactions between other factors (e.g. gender, age, language preference, income, inreach strategy and frequency of clinic visits) will be considered.

Approach, Aim 2 Process Evaluation. Following the RE-AIM framework(41-43), a quasi-experimental process evaluation of intervention programs is proposed as part of the research protocol using validated measures developed in previous studies(44). This process evaluation is designed to examine the intervention’s acceptability, feasibility, and sustainability(45-47). Process measures include: intervention fidelity, recruitment and retention issues, dosage delivered and received, participant satisfaction, and *navigator* perceptions on areas for improvement in each one-on-one session. [name], [name], and [name] will lead trainings to ensure intervention fidelity and standardized intervention delivery and dosage.

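### Holm's step-down procedure on one named primary family would be a cheap gain over the fixed p<0.01 cut-off, which is conservative but not an error

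*Combined protocol and SAP*

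**What the plan says.** Everything at issue is in the combined protocol and SAP, under Analytic approach and sample size, Aim 1.

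- **Sizing.** "We estimated the sample size for 5 comparisons (usual care vs. inreach, usual care vs. outreach, usual care vs. inreach + outreach", plus the combined arm against each single strategy. The level is set by "assuming $\alpha = 0.01$ across all groups", with a power target of at least 0.8. The assumed screening rates are "10% for usual care, 25% for inreach, 25% for outreach, 45% for inreach + outreach combined". The result is 162 per arm, 648 in all, said "to have sufficient power for all primary comparisons of interest".
- **Analysis, no interaction.** Inreach and outreach are each set against usual care, and the rates "will be compared using a Chi-square test of proportions, requiring $p < 0.01$ for statistical significance".
- **Analysis, interaction.** Inreach without outreach and inreach with outreach are each compared with usual care at p<0.025.
- **Either branch.** Combined versus usual care and combined versus each single strategy are listed as secondary, with no cut-off.

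The section names no multiplicity procedure and no overall error rate. It does not require all five comparisons to succeed.

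**The concern.** A level of 0.01 for five tests is a single-step Bonferroni rule: each test faces the same bar whatever the others show. One of the five, combined versus usual care (45% against 10%), is almost certain to succeed, yet in a fixed five-way split its fifth of the alpha is never passed on. Holm's procedure rejects everything the fixed 0.01 rule rejects, can reject more, and holds the familywise error at 0.05 under any correlation among the tests.

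The no-interaction branch is more frugal still. Two tests at 0.01 spend at most 2 × 0.01 = 0.02, while the interaction branch spends 2 × 0.025 = 0.05. Read as pairwise comparisons, the tests that carry Hypotheses 1a and 1b are therefore judged more strictly than the plan's own second branch suggests is necessary. At stake is power that needs no extra patients.

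**Working it through.** **Inputs.** Rates of 10/25/25/45%, 162 per arm, level 0.01 and power 0.8, all from the sizing paragraph. No dropout allowance is needed in the arithmetic, because "Recruitment will continue until a sample size of 162 individuals per group who do not opt out of the research is achieved" (recruitment section). Two assumptions: tests are two-sided (not stated, but this reproduces 162), and overall alpha is 0.05 (not stated, but implied by 5 × 0.01 and 2 × 0.025).

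**1. The plan's own figure.** For 10% versus 25%, the mean rate is 0.175 and the difference 0.15.

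n = [2.576 × √(2 × 0.175 × 0.825) + 0.842 × √(0.10 × 0.90 + 0.25 × 0.75)]² / 0.15² = 148.4

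The continuity correction, n/4 × [1 + √(1 + 4/(n × 0.15))]², gives 161.5, so 162. The figure reproduces. The other pairs need fewer with the same correction: 142 for 25% versus 45%, and 43 for 10% versus 45%.

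**2. The two rules.** Fixed: reject if p<0.01. Holm: order the m p-values and reject the k-th smallest while it is at most 0.05/(m − k + 1), stopping at the first failure. For five tests the steps are 0.01, 0.0125, 0.0167, 0.025, 0.05. For two they are 0.025, 0.05.

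**3. Power by simulation** (four independent binomial arms, pairwise two-sided uncorrected chi-square, at least one million trials):

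| Event | Fixed 0.01 | Holm, five tests |
|---|---|---|
| Each single strategy vs usual care | 0.85 | 0.94 |
| Combined vs each single strategy | 0.89 | 0.96 |
| Combined vs usual care | >0.999 | >0.999 |
| Both single strategies vs usual care | 0.76 | 0.91 |
| Both Hypothesis 1c tests | 0.82 | 0.94 |
| All five | 0.61 | 0.85 |

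If the family is only the two no-interaction tests, Holm also gives 0.94 for each and 0.91 for both.

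With continuity correction, each single strategy against usual care goes from 0.81 to 0.92 (five tests) or 0.93 (two tests). Both 1c tests go from 0.78 to 0.92, and all five from 0.53 to 0.81.

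**4. Which branch would apply.** On the logit scale the planning rates give an interaction of −0.201 with standard error √Σ1/(162·p(1−p)) = 0.399. A test at 0.05 (level and scale assumed) has about 8% power, so the p<0.01 branch would usually apply.

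**5. Interaction branch.** Combined versus usual care is almost certain to be rejected, so Holm in effect tests inreach alone versus usual care at 0.05 instead of 0.025. Formula power rises from 0.91 to 0.95.

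**6. Error.** Across eight global and partial null settings, the highest simulated familywise error was 0.044 for fixed 0.01 and 0.045 for Holm. The rules coincide under the global null. With one true null (inreach at 10%, outreach 25%, combined 45%) the error is about 0.01 for fixed and 0.045 for Holm.

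**7. If arms are pooled.** Hypotheses 1a and 1b (Specific Aims) are worded with or without the other strategy, so the no-interaction tests may be meant as pooled. The factorial margins are then (25 + 45)/2 = 35% against (10 + 25)/2 = 17.5%, with 324 per side. Power at p<0.01 is about 0.995 per test and 0.99 for both. Pooled intervention arms against the usual-care arm alone give above 0.999.

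**8. Sensitivity.** The earlier outreach trial described under Significance had 12.1% screening in usual care. With that rate and the others unchanged, pairwise power for each single strategy is 0.67 under fixed 0.01, and 0.82 (five tests) or 0.83 (two tests) under Holm.

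**The case against.** The strongest reply is that a conservative threshold that meets its own power target is not a fault. That stands. The target reads naturally as per comparison, and fixed 0.01 delivers 0.85, 0.85, >0.999, 0.89 and 0.89. A reader might infer from the 0.61 that the claim of sufficient power fails. The documents do not support this: they never promise joint success, and 0.61 describes the sizing rule only.

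Second, a reader might infer that 0.01 governs all five tests in the analysis. It does not. The analysis paragraph attaches it to two tests, uses 0.025 in the other branch, and sets no cut-off for the secondary contrasts. Holm therefore cannot be specified until the family is settled.

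Third, under pooling the gain for 1a and 1b nearly vanishes (step 7). This stands as a limit on the size. The gain for 1c remains, since that hypothesis asks the combination to beat each strategy alone.

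Fourth, it would be too strong to say that Holm has the same error control. Both rules respect a 0.05 bound, but Holm uses more of it under partial nulls, roughly 0.045 against 0.01 with one true null. The extra power is partly paid for there, still within 0.05.

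**Conclusion.** This is a worthwhile, low-cost improvement, not an error. On the pairwise reading at the planning rates, Holm adds about nine percentage points of power for each single strategy against usual care (0.85 to 0.94) and fifteen for both (0.76 to 0.91). In a five-test family it adds twelve for the Hypothesis 1c pair (0.82 to 0.94). Continuity correction lowers the levels but not the gain.

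The conclusion rests on two-sided tests, an overall 0.05 that the plan implies but does not state, and the planning rates. With pooled arms the benefit is mainly for 1c, and only if the 1c contrasts are in the primary family. The sizing and analysis paragraphs disagree on what is primary, and that has to be resolved first.

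**What to change.** 1. Name one primary family and use it in both the sizing and the analysis paragraphs. State whether the no-interaction tests are pairwise or pooled, and whether the combined-arm contrasts are primary or secondary.
2. Replace the fixed cut-offs with wording such as: *The p-values of the primary family are tested by Holm's step-down procedure at overall two-sided alpha 0.05.* Five tests use 0.01, 0.0125, 0.0167, 0.025 and 0.05; two tests use 0.025 and 0.05. Testing stops at the first non-rejection.
3. Apply the same procedure in the interaction branch in place of two fixed 0.025 tests. That branch names no test of outreach alone versus usual care, which should be settled when the family is named.
4. Keep 648 patients. Restate power under the chosen family and say whether the chi-square test is continuity-corrected.

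**Cost.** A few sentences, written before outcome data are seen, plus the decision on the family. No simple simultaneous confidence intervals match Holm decisions, so report ordinary 95% intervals beside Holm-adjusted p-values. The plan should also acknowledge the fuller use of the 0.05 bound under partial nulls.
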